3.1.2 Stage II

Participants (those identified as the person to receive DAT risk feedback) will include a subset of 10 older adults (65+) drawn from the Stage I Needs Assessment, all of whom have available neuropsychological performance information, magnetic resonance imaging (structural) information, positron emission tomography (PET) amyloid and/or tau information, and apolipoprotein e genetic information already collected as part of UM-MAP, STIM, or DAPPER. Participants will meet all of the inclusion/exclusion criteria applicable for Stage I. Additionally, participants must be negative for mood or anxiety diagnosis and negative on mood measures prior to enrollment in Stage II. Participants must also be currently followed by a medical provider (primary care physician, geriatrician, family doctor). These additional inclusion criteria minimize the likelihood of significant psychological risks following feedback, and facilitate clinical coordination of care between study staff and clinical providers in the event that significant psychological distress does occur.

Co-Participants (those who are currently serving as a caregiver to the participant, or would hypothetically serve in this role should the need arise) include 10 adults, age 18+ years. Similarly, participants must meet criteria from the Stage I Needs Assessment. Additionally, if the participant has

an active legally authorized representative (LAR) or power of attorney (POA) for medical decisions and/or research, that individual must serve in the role of co-participant, and must provide documentation of this legal designation prior to enrollment of the dyad in the study. If the participant does not have an enacted LAR/POA, any individual meeting the above criteria can serve as the co-participant.

All study-related activities will occur at the University of Michigan through virtual visits.

SECTION 3.2 Recruitment Strategy

3.2.1 Stage I: Participants will be recruited from UM-MAP, STIM, or DAPPER. The MADRC recruits participants from several sources including the MADRC Memory Disorders clinic, community screening events, and external referrals. UM-MAP, STIM, or DAPPER participants interested in research are maintained in an IRB-approved database, which is available by request to the PI and her study team.

3.2.2 Stage II: Participants will be recruited to Stage II through invitation, only. The study team will review dyads who complete the Stage I Needs Assessment, screen these cases for any interim changes that might impact eligibility of the participant or co-participant, and contact dyads to determine interest in engaging in the second stage of the study. Specifically, following Stage I, the study team will contact the parent studies (UM-MAP, STIM, and DAPPER) via the MADRC 'cohort discovery' data request pipeline to confirm who among the list of interested Stage I participants have (a) annual research evaluation information with resulting cognitively normal or mild cognitive impairment diagnosis, and (b) at least one of the following: PET amyloid and tau biomarker data, apolipoprotein E genotype, or Neuroquant volumetric neuroimaging from MRI. Of note, none of these biomarker data will actually be accessed by the SHARE(D) research team for recruitment; the actual biomarker and personal health data will be requested only following informed consent from the participant and co-participant.

SECTION 3.3 Procedures

3.3.1 Stage I – for a visual timeline of Stage I Activities, see Figure 1.

Session Description:

[figure not shown]
After telephone screening for eligibility, participants will be scheduled for a study session (ideally in parallel) within approximately one week as availability allows. This session will be 90-to-120-minutes, one-on-one with a study team member.

In March 2020, the global Covid-19 pandemic resulted in research ramp-down and restrictions on in-person research visits. To protect the health of our participants, particularly given their vulnerable status as older adults, we determined that it would be best not to continue in-person research visits, and to instead adapt this protocol to allow for virtual visits. Therefore, during telephone screening, participants will be offered the opportunity to complete the Stage I session as a video or phone visit. Interested participants will be asked whether they have adequate access to and familiarity with a laptop, tablet, or computer to engage in a video visit session in which they will complete questionnaires and interviews using video-conferencing software. Participants who do not have access to this technology or do not feel comfortable completing the visit over video will be offered the opportunity to complete the session over the phone. Those that decline phone or video visit, but remain interested in the study will be deferred for scheduling until a time that it is deemed safe by research administration for participants to engage in in-person research.

In-Person Sessions: At the initiation of the session, participants/co-participants will complete written informed consent and the decision-making tool to ensure that they are cognitively capable of doing so. Additional screening criteria will then be reviewed. Co-participants without recent neuropsychological or cognitive evaluation (within 6 months) will also be screened using the MoCA.

Video Conferencing Sessions: Participants and Co-Participants who are interested in engaging in a video visit will be asked about their access to and comfort with technology for the session prior to scheduling. Participants and Co-Participants must utilize a desktop or laptop computer, or a tablet with a screen at least 9.7 inches in diagonal width to ensure that they are able to view the questions completely. Additionally, participants/co-participants must have access to a stable, secure internet connection (not public wi-fi) and a quiet, private space where they will be uninterrupted for the duration

Figure 1.
Stage I
Timeline of
Activities

of the 2-hour appointment. Participants and Co-Participants who meet the above criteria will be sent separate links to engage in a secure video conference session through the BlueJeans or Zoom for Health applications. Both applications are free, HIPAA-compliant services.

Phone Conferencing Sessions: Participants/co-participants who are interested in engaging in a virtual visit but do not have access to the required technology or otherwise feel uncomfortable with a video visit will be offered the opportunity to complete the session via phone.

Informed Consent for Virtual Visits: The informed consent document will be emailed to participants and co-participants at the time of scheduling, to provide the recipient enough time to review the document. Prior to other study activities, a study team member will set up a phone call to review the consent paperwork together. At this phone appointment, a study team member will explain each section of the informed consent document, pausing to answer questions or clarify misunderstandings. In parallel with the procedures used in in-person sessions, the study team member will also use the Decision-Making Capacity Tool to ensure that the individual providing consent is able to fully understand the decision he/she is making prior to providing consent. After the informed consent document has been reviewed, eligible participants/co-participants will be asked to provide electronic signature on this form. This can be completed through two methods: (a) the patient can download, sign, scan, and email the form back to the study team member, who will additionally sign as witness and study representative, or (b) the SignNow platform will be used to provide electronic consent. SignNow is a secure platform offered through University of Michigan, which is HIPAA-compliant and approved by Health Information Technology Services (HITS). A copy of the form, with all signatures, will be emailed to the participant/co-participant.

Co-Participant Screening for Virtual Visits: As noted above, all co-participants must be cognitively intact based on screening or recent evaluation. In lieu of in-person screening, co-participants will be asked to complete a brief phone or video screen (the Blind version of the Montreal Cognitive Assessment [MoCA]) after informed consent, but prior to other study activities. As with in-person visits, co-participants whose scores fall below the cutoff for impairment will be considered ineligible for study participation. Their respective participants will also be asked to delay scheduling of their virtual visit until they can identify another interested and eligible co-participant.

Ineligible participants or co-participants will be excluded, but paid for their time. Eligible participants and co-participants will be included in the research study, and will continue the session to complete questionnaires and a semi-structured interview. The semi-structured interview will be recorded, as the qualitative responses from participants/co-participants will be analyzed as secondary outcomes in the study. In-person sessions are recorded using a secure, HIPAA-compliant voice recorder, with all sessions transferred to a secure drive, password protected, and deleted from these recorders immediately after the session. Virtual visit interviews will be recorded using BlueJeans, Zoom for Health, or using the voice recorder with the phone call on speakerphone; similarly, these audio files will be de-identified, transferred to a secure drive, and password protected. Participants and co-participants will also complete a Beck Anxiety Inventory and Geriatric Depression Scale – 15 Item after these procedures, in order to monitor anxiety and mood (see Section 3.5.1 Monitoring). All in-person sessions will take place in the PI's (ARF) laboratory at the University of Michigan. All virtual sessions will be completed by study team members either at the [name] laboratory, or in a secure, private location. Individuals will receive \$20 compensation for their participation in the study, paid via check after the session.

Conceptual Model. The conceptual model for understanding feedback preferences is adapted from the Health Belief Model³⁰, (Figure 1). The resulting model contains three domains: 1) Perceived Threat of AD (i.e., perceived vulnerability to and seriousness of an AD diagnosis); 2) Feedback Expectancies

(i.e., rationale for learning about risk, perceived barriers to learning about or dealing with risk information); and 3) Feedback Preferences (i.e., the type of risk disclosure desired).

Primary Outcomes:

Questionnaires: In addition to the qualitative information gathered during the semi-structured interviews (see below), several formal questionnaires will be administered to provide quantitative information:

[figure not shown]

Figure 2. Conceptual Model for Risk Disclosure Preferences

HBM Components. We have developed the Anticipatory Dementia Inventory (ADI), a 50-item Likert-style measure of DAT-specific worry based on the HBM. Items relate to perceived vulnerability to DAT, perceived seriousness of a diagnosis, and expectations about ability to deal with a diagnosis, with responses ranging from strongly disagree to strongly agree. This measure has previously been validated for use with racially diverse older adults through the PI’s graduate work (paper in preparation).

Knowledge of AD/DAT. DAT knowledge will be measured through a multiple-choice quiz about DAT symptoms, course, causes, treatments, and risk factors. This quiz will be developed in Quarter 1 of the first funding year via monthly study-team meetings.

Risk Disclosure Interest and Preferences. In addition to the open-ended preference/rationale questions administered in the interview, we will utilize a questionnaire asking participants and co-participants to rate their level of interest in receiving feedback based on each risk factor (Table 3; e.g., “How interested are you in knowing about your/your family member’s risk for Alzheimer’s Dementia based on your genotype?”), on a continuous scale ranging from 1 (no interest) to 5 (very interested). Participants and co-participants will also use a checklist to state which information they would want to receive, selecting as many of the DAT risk information sources as desired (e.g., “Would you choose to receive feedback about your/your family member’s risk for DAT based on genotype? Yes or No?”)

Risk Disclosure Rationale. Participants will also be provided with a list of reasons for risk disclosure cited in prior literature and asked to rank the primary reason/purpose for risk disclosure.

Importance of Risk Disclosure Elements. Participants and co-participants will also complete a questionnaire asking them to rate the importance of different empirically supported elements of risk disclosure protocols cited in the published literature (e.g., How important do you think it is that educational materials are provided as part of your risk disclosure feedback?). Responses will be on a continuous scale from 1 (not at all important) to 5 (extremely important).

The order of questionnaires and interview questions will be counter-balanced to avoid potential reciprocal priming effects (e.g., discussing perceived vulnerability to DAT may influence feedback preferences).

For video sessions, the above questionnaires will be presented as Microsoft Powerpoint slide shows, with one question on each slide. The study team member will share his/her screen, and advance the slideshow, asking each questions clearly, to facilitate ease of comprehension for participants.

Secondary Outcomes:

Semi-Structured Interviews: Although the quantitative methods above will be the primary source of information for the current project, we believe that the inclusion of qualitative methods will provide richness and context to the results. Furthermore, the inclusion of open-ended questions and qualitative coding methods will remove bias against minorities implicit in validated measures and allow for identification of risk disclosure concepts or perspectives not covered in these measures. The interviews will incorporate risk disclosure questions adapted from Co-Investigator [name]' Risk Evaluation and Education in Alzheimer's Disease (REVEAL) Study, a successful multi-site trial of risk disclosure needs in older adults. We will also include novel questions that relate to the three domains of the HBM to study patient and co-participant characteristics that influence preferences. During the interview, they will have the opportunity to freely discuss what sources of DAT risk they would prefer to receive about themselves or, in the case of co-participants, about their loved ones, and how they plan to use that specific risk information. This open-ended approach will not limit responses to only presumed reasons for risk disclosure drawn from the past literature.

[figure not shown]
3.3.2 Stage II - for a visual timeline of Stage II Activities, see Figure 3.

Preliminary Screening: Following study team review of the participant's and co-participant's medical record to ensure no interim changes make either part ineligible, the study team will also access the participant's prior MADRC study involvement to determine whether they have adequate information for risk disclosure. Specifically, the study team will communicate with the MADRC UMMAP, STIM, and DAPPER teams to determine if the participant has (a) complete cognitive testing and research diagnosis and (b) recent (within 12 months) data for at least one additional biomarker, including MRI Neuroquant reports, PET amyloid and tau, or APOE genetic results. If the participant meets these criteria, the study team will send an email introducing the study (see 'SHARE(D)' Stage II Email Script') and begin contacting the participant via phone (see 'SHARE(D)' Stage II Oral Script').

Informed Consent for Virtual Visits: The informed consent document will be emailed to participants and co-participants at the time of scheduling, to provide the recipient enough time to review the document. Prior to other study activities, a study team member will set up a phone call or video session to review the consent paperwork together. At this phone appointment, a study team member will explain each section of the informed consent document, pausing to answer questions or clarify misunderstandings. The study team member will also use the Consent Decision-Making Capacity Tool to ensure that the individual providing consent is able to fully understand the decision they are making prior to providing consent. After the informed consent document has been reviewed, eligible participants/co-participants will be asked to provide electronic signature on this form. This can be completed through two methods: (a) the patient can download, sign, scan, and email the form back to the study team member, who will additionally sign as witness and study representative, or (b) the Signnow platform will be used to provide electronic consent. SignNow is a secure platform offered through University of Michigan, which is HIPAA-compliant and approved by Health Information Technology Services (HITS). A copy of the form, with all signatures, will be emailed to the participant/co-participant. Only following receipt of this informed consent document will actual biomarker data be requested and received from the parent study teams (UMMAP, STIM, DAPPER) for integration into the disclosure protocols.

Additional Screening & Scheduling: Following receipt of the signed informed consent documents, both the participant and co-participant will be asked to complete the GDS-15 and BAI via phone or video (these can be conducted on the same call used to complete the consent documentation). Any individuals who score above the cutoffs for these measures will be ineligible to take part in the study, per eligibility criteria noted above. Additionally, all co-participants must be cognitively intact based on screening or recent evaluation. Co-participants who do not have recent screening or cognitive testing in their medical/research records will be asked to complete a brief phone or video screen (the Blind version of the Montreal Cognitive Assessment [MoCA]) on this call. Co-participants whose scores fall below the cutoff for impairment will be considered ineligible for study participation. Their respective

Figure 3. SHARE(D) Stage II Timeline of Activities

participants will also be asked to delay scheduling of their virtual visit until they can identify another interested and eligible co-participant. Once this secondary screening of the dyad has been completed, the study team will schedule all three sessions for each subject.

Session Description:

Education & Disclosure Session:

During this session, participants and co-participants will complete the following steps, summarized in Table 2:

1. Educational Module – participants and co-participants will be shown an interactive presentation covering the following topics:
 - a. Alzheimer’s disease
 - b. Dementia-Alzheimer’s Type
 - c. Available treatments for AD/DAT
 - d. Available biomarkers or indicators of DAT risk: how they are collected, what information is shared, and what the meaning of this information is relative to risk for AD and DAT
 - e. Risks of learning one’s personal DAT biomarker status
 - f. Benefits of learning one’s personal DAT biomarker status

This module will include multiple opportunities for either member of the dyad to ask questions.

2. Disclosure Preferences & Decision-Making Capacity Assessment – The educational module contains several ‘checks for understanding’ after each section to determine whether the participant fully demonstrates decision-making capacity for risk disclosure. As

per the Disclosure Decision-Making Assessment Tool (DDMAT), the study team member will make notes about the participant’s responses, provide corrections, clarifications, or prompts if needed, re-assess after this additional information has been provided, and then assess whether the ultimate

response demonstrates full understanding, appreciation, rationale, and communication (elements of decision-making capacity).

Of note, if the participant has a LAR/POA co-participant, that individual must demonstrate decision making capacity for the participant to receive risk disclosure, and agree with this decision. Regardless of whether the LAR/POA wants the participant to complete risk disclosure, the study team will not move forward with sharing the participant's risk information with either party unless assent is provided by the participant.

If the participant or designated LAR/POA does not demonstrate full decision making capacity, the study team will not move forward with risk disclosure, and the dyad's involvement in the study will be complete.

3. Risk Disclosure: the study team have developed a flexible disclosure protocol that provides written and graphic representations of the participant's health information and risk indicators. The protocol will be adapted using standardized instructions prior to the session, to personalize each protocol to the participant. Personalization will be based on demographic factors and geographic location of the patient's home (to ensure identified resources are close by and accessible), and research diagnosis and level of risk (to ensure that appropriate recommendations and resources are given). Additionally, we will adapt the protocol based on which of the following indicators the participant and/or LAR/POA requested after the education module (provided these are available from prior study participation):
 - **DAT risk based on standard clinical procedures**: a review of cognitive strengths, weaknesses, and impairments relative to age-, sex- and/or race-matched normative data (using qualitative ranges from severely impaired to above average), in the context of the participant's medical and family history; disclosure of clinical research diagnosis (cognitively healthy or MCI); qualitative discussion about the increased risk for conversion to dementia based on an MCI diagnosis
 - **AD risk based on apolipoprotein-e ϵ 4 genotype**: disclosure of genotype (ϵ 4 positive [homozygous/heterozygous] or negative); quantitative (percent or odds ratio) risk for Alzheimer's disease based on lifetime cumulative risk curves integrating race, gender, and genotype information (REVEAL study³¹)
 - **AD risk based on structural T1/T2/FLAIR magnetic resonance imaging (MRI)***: quantitatively graded interpretation of atrophy (primarily in mesial temporal structures) based on age- and sex-matched normative comparisons drawn from the Neuroquant/Lesionquant program (Cortech labs: <https://www.cortechlabs.com/products/neuroquant/>); disclosure of any incidental findings; qualitative discussion regarding risk of underlying AD pathology based on imaging, and associated potential for DAT.
 - **AD risk based on positron emission tomography (PET) amyloid and tau***: qualitative interpretation (i.e., Elevated vs. Not Elevated) of the presence or absence of significant burden for either of the abnormal proteins; discussion that elevation on either/both proteins may indicate underlying AD pathology that may or may not develop into DAT.

*Given the lack of validated quantitative models of DAT risk conferred by these factors⁸, only qualitative information regarding risk for developing or converting to DAT (the phenotypic presentation of AD) will be provided at this time. Particular attention will be given to differentiating the presence of AD pathology (i.e., positive amyloid and tau burden or indications of significant atrophy) from the actual development of symptoms (aMCI, DAT).

The disclosure protocol includes a summary of the above indicators; however, no summative or combined risk estimate is provided, as such an estimate is not empirically supported. Following this summary, the protocol includes general recommendations and next steps for healthy aging (e.g., taking care of physical and emotional health, staying cognitively and socially engaged) and a list of informational and support resources. As with the Education Module, the disclosure protocol will include multiple 'checks for understanding' after each section to ensure that information communicated is being comprehended accurately by the participant and co-participant.

4. Immediately following risk disclosure, the participant and co-participant will complete outcome measures and a brief psychological risk assessment with a clinical psychologist utilizing the recall assessment and impact of events scale documents. Both parties will also complete a checklist of requested resources or supports from the region- and service-specific list developed in SHARED Stage I. Participants and/or LAR/POAs will also be asked whether they would like a written summary of the information provided; if so, this report will be prepared after the visit and sent via mail to the participant or LAR/POA. No results will be uploaded in the participant's medical record; however, they are welcome to share the results with their medical providers independently.

Table 2. Proposed Order & Components of Disclosure Sessions
1. Initial Consent
2. Education Module
3. Assessment of Disclosure Preferences
4. Assessment of Disclosure Decision-Making Capacity
5. Personal Risk Disclosure 
 - Clinical Predictors of DAT Stage (Cognitive Testing, Research Diagnosis) - Structural MRI-conferred AD Risk (qualitative) - APOE-conferred AD Risk (quantitative) - PET Amyloid and Tau-conferred AD risk (qualitative)
6. Recommendations
7. Participant & Caregiver Resources
8. Risk Assessment & Follow-Up (as needed)
9. Outcomes Assessment 
 - Comprehension - Mood/Psychological Satisfaction (exploratory)

Follow-Up Sessions:

Outcome measures and psychologist risk assessment will also be repeated at 1-week and 6-weeks post-feedback. Participants and co-participants will also be encouraged to call the PI (ARF) or ML with any additional concerns or questions between these sessions. All sessions will take place in via phone or virtual visit. Participants and/or co-participants who complete some but not all sessions will receive pro-rated payment (\$10 per session, \$30 total), paid as a check after the sessions.

Primary Outcomes

Comprehension and recall of personal risk disclosure information will be measured as accuracy scores on a series questions about the patient's results and the meaning of different messages provided during feedback in regards to AD/DAT risk (i.e., "My Attention was [Normal/Impaired/Don't Know]"). The questionnaire will result in two scores: a Personal Information score and a Meaning of Information score (as it is possible that an individual may accurately remember his/her own information, but misinterpret it, or may understand the meaning of risk information, but incorrectly recall his/her own feedback).

Psychological reactions to personal risk disclosure information will be measured both in terms of general mood and anxiety, as well as feedback-specific distress.

Depression: Mood will be assessed using the self-administered Geriatric Depression Scale – Short Form (GDS-15)³²⁻³³. The GDS-15, a 15-item assessment of depressive symptoms, has been adapted to remove common depression symptoms often conflated with normal aging (i.e.,

somatic symptoms). It asks the participant to rate the presence of mood symptoms over the past two weeks.

Anxiety: The BAI³⁴, also validated for use with older adults³⁵ is a 21-item measure of the perceived severity ('not at all' to 'severely') at which the participant is experiencing anxiety symptoms over the past week.

Feedback-Specific Distress: We will utilize a revised version of the Impact of Genetic Testing for Alzheimer's Disease (IGT-AD) Scale, which itself is based on The Impact of Event Scale (IES)³⁶. The scale will be specifically anchored to the 'life event' of receiving feedback; responses will be slightly modified to assess the impact of receiving any and all AD indicator results (not solely genetic information). The IES and IGT-AD have been utilized to measure test-related distress in previous risk disclosure studies³⁷⁻³⁹, including REVEAL. Participants who have a negative score of 24 or more will be contacted by PI for follow-up with participant/co-participant.

Exploratory Outcomes

Satisfaction with the feedback process will be evaluated by determining how well participants' and informants' pre-test expectations are met. We will collect subjective, open-ended qualitative ratings of the utility of risk assessment using questions developed in the REVEAL study, such as "What was the overall impact that your risk information had on you?", "Would you recommend risk assessment for AD to your family or friends?", and "If you had it to do over again, would you choose to have risk assessment for AD?"

SECTION 3.4 DATA MANAGEMENT & ANALYSIS

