The few studies examining risk disclosure preferences in non-White populations^{16-17,23-24} suggest that African-American individuals are more likely than White counterparts to decline feedback about DAT risk. More nuanced preferences about amount, type, and reasons for feedback in African-American versus White participants remain unknown. Similarly, the *reasons* behind this discrepancy have never been directly studied. For White participants, personal characteristics such as general or dementia-specific anxiety^{6,18,24,25} and knowledge of AD biomarkers, symptoms, course, treatments^{24,25} influence preferences for type and amount of feedback. These same factors – perceived vulnerability to DAT and DAT knowledge – appear to be lower in African-American individuals²⁴ but it is unclear if these group differences drive the decreased desire for DAT risk disclosure. We will directly evaluate patient characteristics that contribute to feedback preferences in a sample of African-American and White participants using an application of the Health Belief Model (HBM)²⁶. More specifically, we will study how perceived vulnerability to DAT, perceived seriousness of DAT, perceived benefits of DAT risk disclosure, and perceived barriers to effectively using DAT risk information shape feedback preferences.

Need 3: Our ability to effectively communicate DAT risk to participants and informants is limited by a lack of empirically-supported methods that integrate multiple risk factors. Existing studies have often taken a “siloed” approach that fails to integrate the multiple sources of DAT risk. Several studies have analyzed pre-disclosure desire to learn about a specific risk factor^{6,7,16-18}, or reactions to real¹² or simulated¹² single-source risk disclosure. Many provide guidelines for single risk-factor feedback^{7,12,27-30}, though these suggestions are abstract and drawn from investigations of mostly White, highly educated participants. To date, no study has developed a feedback protocol that integrates multiple DAT risk factors (clinical, genetic, neuroimaging, and biomarker) and can be adapted to meet the needs of racially diverse patients.

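### Stage II data requirements differ between sections 3.1.2, 3.2.2 and 3.3.2, so the plan does not fix which risk sources must be available for the 10 pilot participants

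*Combined protocol and SAP*

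**What the plan says.** Three places in the combined protocol and SAP state which data a Stage II participant must already have.

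- **Section 3.1.2 (eligibility)** describes the 10 participants as "all of whom have available neuropsychological performance information, magnetic resonance imaging (structural) information, positron emission tomography (PET) amyloid and/or tau information". The same sentence also requires the APOE genotype from the parent study. This is a conjunction: cognition, MRI, PET and APOE.
- **Section 3.2.2 (recruitment)** asks for an annual research evaluation with a diagnosis of normal cognition or MCI, and "at least one of the following: PET amyloid and tau biomarker data, apolipoprotein E genotype, or Neuroquant volumetric neuroimaging from MRI".
- **Section 3.3.2 (Preliminary Screening)** asks for complete cognitive testing and a research diagnosis, and "recent (within 12 months) data for at least one additional biomarker, including MRI Neuroquant reports, PET amyloid and tau, or APOE genetic results". It continues: "If the participant meets these criteria, the study team will send an email introducing the study".

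Three further passages bear on the consequence. In section 2.1, Need 3 says that "no study has developed a feedback protocol that integrates multiple DAT risk factors" and names clinical, genetic, neuroimaging and biomarker sources. Section 3.3.2 (Risk Disclosure) discloses only indicators that the participant or legal representative asked for and that exist from the parent study. Section 3.4.2.2 totals the two accuracy scores (Personal Information and Meaning of Information), summarises them by mean, median and standard deviation, and adds an exploratory look at which types of information were better understood.

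**The concern.** The sections admit different people. A participant with cognitive testing and APOE alone satisfies 3.2.2 and, if the result is recent, 3.3.2, but fails 3.1.2. A participant with MRI, PET and APOE all more than 12 months old satisfies the data requirement of 3.1.2 but fails 3.3.2. PET is also worded differently: amyloid and/or tau in 3.1.2, amyloid and tau in the other two.

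The looser rule cannot be read as a pre-screen that a later step tightens. Section 3.3.2 presents its check as the test of whether there is enough information for disclosure, and passing it triggers contact. The later Additional Screening & Scheduling step covers mood, anxiety and co-participant cognition, and does not check for the remaining sources.

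Two things depend on this. One is who may be enrolled, and hence how much of the multi-source integration described in section 2.1 the pilot can exercise. The other is what the recall totals mean: if people are told about different numbers of sources, a pooled total covers different content in different people, and section 3.4.2.2 states no denominator for this.

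**Working it through.** The plan gives no figure to reproduce, because Stage II is descriptive and has no sample-size calculation. The check compares the rules directly.

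**Step 1. Profiles admitted, three biomarker types.** Take cognition as present and code MRI, APOE and PET as present or absent: 2³ = 8 profiles.
- At least one (3.2.2; 3.3.2 before its time limit): 8 − 1 = 7 profiles.
- All three (3.1.2): 1 profile.
- Admitted by the looser rule only: 7 − 1 = 6.

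**Step 2. Amyloid and tau coded separately.** Now 2⁴ = 16 profiles.
- 3.1.2 (MRI, APOE, and amyloid and/or tau): 3 profiles.
- 3.2.2 (MRI, or APOE, or both tracers): 16 minus the 3 profiles with neither MRI nor APOE and at most one tracer = 13.
- All 3 lie within the 13, so 13 − 3 = 10 qualify under 3.2.2 only.
- PET wording: with and/or, 3.2.2 would admit 15 rather than 13. The 2 extra profiles have a single tracer and neither MRI nor APOE. With both tracers required, 3.1.2 would admit 1 profile rather than 3.

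These are counts of profiles, not of people.

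**Step 3. What each rule guarantees across 10 participants.**
- 3.1.2: 10 × 3 = 30 biomarker-type results available.
- At least one: 10 × 1 = 10 guaranteed, with a range of 10 to 30. Any one type could be absent in all 10.

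**Step 4. Illustration under the at-least-one rule.** The documents give no availability rates. Assume that each type is independently available with the same probability p, and condition on having at least one:
- expected number with all three = 10·p³ / (1 − (1 − p)³)
- expected number with two or more = 10·(3p²(1 − p) + p³) / (1 − (1 − p)³)

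| p | P(at least one) | All three, of 10 | Two or more, of 10 |
|---|---|---|---|
| 0.5 | 0.875 | 10 × 0.125/0.875 = 1.4 | 10 × 0.500/0.875 = 5.7 |
| 0.8 | 0.992 | 10 × 0.512/0.992 = 5.2 | 10 × 0.896/0.992 = 9.0 |
| 0.9 | 0.999 | 10 × 0.729/0.999 = 7.3 | 10 × 0.972/0.999 = 9.7 |

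The table counts availability. The number of sources actually disclosed can only be equal or lower, because dyads choose among the available indicators.

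**The case against.** The strongest reply is that variable content is intended. Objective 2 (section 2.2) aims at protocols for different combinations of risk factors, and section 3.3.2 tailors disclosure to what was requested and is available. On that view the at-least-one rule is the real one and 3.1.2 is loosely worded. This may be so, but then 3.1.2 is wrong as it stands and needs correcting. The argument settles which text to change, not whether to change it.

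It does limit the point in one important way. Even if all 10 participants had every source, dyads could ask for different subsets, so an all-source rule would not by itself equalise the content behind the recall totals. That part stands.

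Three stronger readings are tempting, and the documents do not support them.
- *The three sections cannot all be followed.* They can. A participant who has every source, with at least one biomarker within 12 months, meets all three. What is undefined is whether others may enter.
- *Some participants would have only one risk source.* No. Sections 3.2.2 and 3.3.2 require the cognitive evaluation as well, and Table 1 treats standard clinical information as a source in its own right. At least two sources are always available.
- *Few dyads would have more than one biomarker.* Availability is not stated, and in the illustration most dyads have two or more at every value of p shown.

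Finally, the stakes are modest. Stage II is a 10-dyad, single-group pilot with descriptive analysis, and the comparison by information type is exploratory. No error rate or power figure is affected.

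**Conclusion.** The inconsistency is real and lies in the current text: the data requirement for Stage II is wrong in at least one of the three sections, and nothing in the plan ranks them. In guaranteed availability, the difference is three biomarker types per participant against one, or 30 results against 10 across the pilot. That follows from the text alone. The figures of 5.7 to 9.7 of 10 with two or more types, and 1.4 to 7.3 with all three, rest on assumed independent and equal availability of 50% to 90%. They show that the outcome depends on a quantity the plan does not give.

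A reader might infer that the pilot will fail to test multi-source disclosure. The documents do not support that. They support the narrower conclusion that the extent of multi-source disclosure is left open by the eligibility text and by participant choice, and that the pooled totals in section 3.4.2.2 would not show it. The point is worth correcting because it changes who may be enrolled and how the recall scores are read.

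**What to change.** 1. Reconcile sections 3.1.2, 3.2.2 and 3.3.2 to one data-availability rule, one PET wording and one recency limit. State whether the limit applies to every source, including genotype, which section 2.1 itself describes as static.
2. Whichever rule is kept, report for each dyad the number and type of sources actually disclosed.
3. In section 3.4.2.2, report the Personal Information and Meaning of Information scores as percent correct per source, each with its own n, rather than only as pooled totals.
4. Describe findings on integrated disclosure by the number of dyads who actually received two or more biomarker sources.

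The cost is amendment wording and a little extra descriptive analysis. An all-source rule may shrink the pool drawn from up to 60 Stage I dyads; an at-least-one rule may narrow what can be claimed about integration. Items 2 to 4 can still be done after enrolment, provided that the sources disclosed and the item-level answers were recorded.
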